1. TAK-385
 - 1) Run-in
Administration of TAK-385 placebo tablets should be started on the day of VISIT 2. Until the day before VISIT 3, subjects take 1 tablet once daily before breakfast. The investigator or designee must instruct the subject to bring each of the study drug containers (blister cards) to each visit, regardless of whether the study drugs are empty.
 - 2) Treatment
Administration of TAK-385 40 mg tablets or TAK-385 placebo tablets should be started on the day of VISIT 3. Until the day before VISIT 10, subjects take 1 tablet once daily before breakfast.

CONFIDENTIAL

During the Treatment, subjects should try to make each scheduled visit to the study site in the morning and take the TAK-385 (40 mg or placebo) tablet for the day after completing the scheduled tests (see Section 7.4). However, if unable to visit the study site in the morning of VISIT 4, 5, 6, 7, 8 or 9, subjects should take the morning dose before breakfast and report to the investigator or subinvestigator that the morning dose has been taken (see Section 7.4).

2. Leuprorelin
 - 1) Run-in
- 1) Run-in

The investigator or subinvestigator will decide the dosage of leuprorelin acetate (1.88 mg or 3.75 mg) injection for individual subjects at VISIT 2 (see Section 6.1.2 for details). Leuprorelin acetate (1.88 mg or 3.75 mg) placebo injection should be administered SC on the day of VISIT 2.

- 2) Treatment

Leuprorelin acetate (1.88 mg, 3.75 mg, 1.88 mg placebo, or 3.75 mg placebo) injection are administered SC once every 4 weeks on the day of visiting the study sites. At VISIT 4, leuprorelin acetate (1.88 mg, 3.75 mg, 1.88 mg placebo, or 3.75 mg placebo) injection should NOT be administered.

For dosing, powder in a vial should be sufficiently suspended with the vehicle for suspension (1 mL). A needle for injection of 23 Gauge or larger should be used. For optimal SC injection, need to follow the following instructions.

- The site for SC injection should be the brachial, abdominal or gluteal region.
- The injection site should be changed each time. Repeated injection should not be given at the same site.
- Confirmation should be made to see that the needle is not piercing a blood vessel.
- The patients should be instructed not to massage the injection site.

Instructions for preparing method of leuprorelin acetate (1.88 mg or 3.75 mg) injection and leuprorelin acetate (1.88 mg or 3.75 mg) placebo injections are as follows.

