9.3.3 Final Visit or Early Termination

9.3.3.1 VISIT 10 (Day 169) (or Early Termination)

The final visit during the Treatment will be performed on VISIT 10 (169 days after the initial dose of the study medication for the Treatment). The following procedures should be performed. If early termination occurs during the Treatment, the same procedures scheduled at VISIT 10 should be performed.

- Pregnancy test (urine)
- Physical examination
- Vital signs and weight
- Patient diary (collected)
- Transvaginal ultrasound (see Section 9.1.17).
- BMD
- UFS-QOL
- WPAI:GH
- Anemia-related measurements
- Clinical laboratory tests

- Pharmacodynamic measurements
- Biochemical bone metabolism markers
- Standard 12-lead ECG
- AE
- Concomitant medications
- Compliance of study drug administration
- PGx sample collection (perform only in subjects who consent and from whom the sample has not been collected [see Section 9.1.12])

For all subjects receiving study medication, the investigator or subinvestigator must complete the Subject Status eCRF page.

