9.3.4 Follow-up

9.3.4.1 VISIT 11 (Final visit of the Follow-up, 28 days after last dose)

The Follow-up lasts for 4 weeks (28 days) from the day after the final dose of study drug. The following procedures should be performed at the final visit of the Follow-up (VISIT 11). If early termination occurs during the Treatment, the same procedures scheduled at VISIT 11 should be performed 4 weeks (28 days) after the end of treatment. If study termination occurs during the Follow-up, the same procedures scheduled at VISIT 11 should be performed.

- Pregnancy test (urine)
- Physical examination
- Vital sign and weight
- Status of menstruation recovery
- UFS-QOL
- Anemia-related measurement
- Clinical laboratory test
- Pharmacodynamic measurement
- Standard 12-lead ECG
- AE
- Concomitant medications
- PGx sample collection (perform only in subjects who consent and from whom the sample has not been collected [see Section 9.1.12])

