10.2 Procedures

10.2.1 Collection and Reporting of AEs

10.2.1.1 AE Collection Period

Collection of AEs will commence from the time the subject signs the informed consent. Routine collection of AEs will continue until VISIT 11 (or early termination).

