7.1.1 Study Definitions

Duration of exposure to double-blind study drug (days) :

Date of last dose of double-blind study drug - date of first dose of double-blind study drug +
1

Double-blind study drug compliance (%) :

Number of TAK-385 blinded drugs taken/duration of exposure to TAK-385 blinded drug *
100 (rounded to 1 decimal places)

Disease duration (years):

((year of informed consent*12 + month of informed consent) -(year of first defined diagnosis of uterine fibroids*12 + month of first defined diagnosis of uterine fibroids))/12 (rounded to 1 decimal places)

Maximum drug holidays (days):

Maximum number of consecutive days on which the subject does not take the TAK-385 blinded drug for the treatment period

Total PBAC score from Week 6 to 12

Total PBAC score from Day 43 to earlier of Day 84 or Follow-up Day 3.

Similarly, Total PBAC score from Week 2 to 6 and from Week 18 to 24 will be defined as

those from Day 15 to earlier of Day 42 or Follow-up Day 3 and from Day 127 to earlier of Day 168 or Follow-up Day 3, respectively.

Total PBAC score for 6 weeks before the final dose of study drug

Total PBAC score for the last 42 days of the treatment

NRS score from Week 6 to 12

Average NRS score from Day 43 to earlier of Day 84 or Follow-up Day 3.

Similarly, NRS score from Week 2 to 6 and from Week 18 to 24 will be defined as average NRS score from Day 15 to earlier of Day 42 or Follow-up Day 3 and from Day 127 to earlier of Day 168 or Follow-up Day 3, respectively.

NRS score for 6 weeks before the final dose

Average NRS score for the last 42 days of the treatment

Total PBAC at baseline

Total PBAC score from first day of menstrual period confirmed at Visit 2 to a day prior to menstrual period confirmed at Visit 3

NRS score at baseline

Average NRS score from first day of menstrual period confirmed at Visit 2 to a day prior to menstrual period confirmed at Visit 3

Use of analgesic medications during the treatment from Week 6 to 12

((number of days with analgesic medications use between Day 43 and earlier of Day 84 or Follow-up Day 3)/(number of days with available data between Day 43 and earlier of Day 84 or Follow-up Day 3))*100 (rounded to 1 decimal places)

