7.1.2 Definition of Study Days

When calculating Study Day relative to a reference date (ie, date of first dose of double-blind study drug [Day 1]) , if the date of the observation is on the same date or after the reference date, it will be calculated as: date of observation - reference date + 1; otherwise, it will be calculated as: date of observation - reference date. Hence, reference day is always Day 1 and there is no Day 0.

When calculating Follow-up Day relative to a reference date (ie, date of last dose of double-blind study drug [Follow-up Day 0]) , it will be calculated as: date of observation - reference date. Hence, reference day is always Follow-up Day 0.

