A subject with a TEAE that occurs in more than one interval is counted in all the intervals that the TEAE occurs. For each time interval, a subject with multiple occurrences of TEAE within a SOC or a PT will be counted only once in that SOC or PT.

When calculating percentages for each time interval, the number of subjects at risk (ie, subjects who either have an exposure or have an occurrence of TEAE, during or after the corresponding time interval) will be used as the denominator. The number of subjects whose onset of any one of the TEAEs is within the time interval will be used as the numerator.

- Summary table for (10)

Most frequent TEAEs refer to PTs whose percentages are at least 5.0% in any one of the treatment groups.

- Summary table for (11)

Most frequent Non-Serious TEAEs refer to PTs whose percentages are at least 5.0% in any one of the treatment groups. If no Non-Serious TEAEs exceed a frequency of 5.0%, the frequency cutoff of 2.0% will be used instead. Percentages will be based on the number of subjects in the safety analysis set.

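### In the TEAE-over-time table, the Day 169-to-Max denominator leaves out women still under AE collection who have neither a dose nor a TEAE on or after Day 169, so that column's percentages are expected to be too high

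*SAP*

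**What the plan says.** SAP 7.11.1.2 plans summary table (9), TEAEs by system organ class and preferred term over time. It uses 28-day onset intervals up to Day 168 and a last, open-ended interval from Day 169 to Max.

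- **Denominator:** the number at risk, meaning "subjects who either have an exposure or have an occurrence of TEAE, during or after the corresponding time interval".
- **Numerator:** "The number of subjects whose onset of any one of the TEAEs is within the time interval will be used as the numerator".
- **Exposure:** SAP 7.1.1 measures its duration by dosing dates, as "Date of last dose of double-blind study drug - date of first dose of double-blind study drug" plus 1, with no period added after the last dose.
- **Day count:** SAP 7.1.2 sets the first double-blind dose as the reference: "Hence, reference day is always Day 1 and there is no Day 0".
- **Last tablet:** Protocol 8.1.3 says "Until the day before VISIT 10, subjects take 1 tablet once daily before breakfast". The heading of Protocol 9.3.3.1 and the visit windows in SAP 7.1.3 put VISIT 10 on Day 169.
- **AE collection:** Protocol 10.2.1.1 continues it to VISIT 11 (or early termination). Protocol 9.3.4.1 states: "The Follow-up lasts for 4 weeks (28 days) from the day after the final dose of study drug".
- **TEAE definition:** Protocol 13.1.5 counts any AE with onset on or after the start of Treatment drug, with no upper limit. It also lists TEAEs over time among the safety displays.

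**The concern.** Whether a woman is in a denominator should not depend on whether she had the event being counted. In the last column it does. A woman who finishes on schedule is observed for about four weeks after her last tablet. The rule counts her if she has a TEAE in those weeks and drops her if she does not.

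One day of visit timing can decide it. Take two completers with no TEAE on or after Day 169. The one seen on Day 169 took her last tablet on Day 168 and is left out. The one seen on Day 170 took a tablet on Day 169 and is counted. Both are followed for about 28 days.

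Protocol 6.2.1 says the Follow-up is there for safety assessment, and table (9) is the only planned TEAE table split by onset time. An inflated last column beside earlier columns that are little affected could be read as a rise in events after treatment stops.

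**Working it through.** The plan gives no figure for this column, so there is none to reproduce. The check is on the timeline and then on the arithmetic of the rule.

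**Timeline.** VISIT 10 on Day 169 puts the last tablet on 169 − 1 = Day 168. The sixth and last scheduled injection is on 1 + 5 × 28 = Day 141. Follow-up ends on 168 + 28 = Day 196. A woman on schedule is thus observed from Day 169 to Day 196 with no dosing date in that interval.

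**Notation, among women under AE collection on or after Day 169:**
- f = share with a dose on or after Day 169 (assumed; not in the documents)
- r = true share with a TEAE onset on or after Day 169 (assumed; not in the documents)
- g = share with an earlier TEAE still ongoing on Day 169 (assumed; not in the documents)

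**Reading A: occurrence means onset.** Under independence, shown % = r / [f + (1 − f)r].

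**Reading B: occurrence also covers ongoing TEAEs.** Under independence, shown % = r / [1 − (1 − f)(1 − r)(1 − g)].

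Any-TEAE row with r = 20% (the correct value is 20%) and g = 40% for reading B:

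| f | A: denominator share | A: shown | B: denominator share | B: shown |
|---|---|---|---|---|
| 25% | 0.40 | 50.0% | 0.640 | 31% |
| 50% | 0.60 | 33.3% | 0.760 | 26% |
| 75% | 0.80 | 25.0% | 0.880 | 23% |
| 90% | 0.92 | 21.7% | 0.952 | 21% |

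**In counts (reading A).** Take 130 followed women (assumed), 26 with a TEAE and f = 50%. The denominator is 65 dosed women plus 20% of the other 65, that is 65 + 13 = 78. The table shows 26/78 = 33.3% instead of 26/130 = 20%, and 52 followed women are missing.

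**Sensitivity (reading A):**
- *Without independence:* the denominator share lies between max(f, r) and min(1, f + r). The shown value then lies within 44–80%, 29–40%, 21–27% and 20–22% at the four values of f.
- *Other true rates:* for r = 10% and 40%, the column shows 18.2% and 57.1% at f = 50%, and 11.0% and 42.6% at f = 90%.
- *A single preferred term:* with a true 5% and r = 20%, it shows 12.5%, 8.3%, 6.3% and 5.4%.
- *Between arms:* the inflation depends on each arm's own r. At f = 25%, true values of 10% and 20% show as 0.10/0.325 = 30.8% and 0.20/0.40 = 50.0%.

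**The case against.** **Many women may be dosed on or after Day 169.** This stands as a limit on size. SAP 7.7 has an exposure category of 169 days or more, and the Week 24 windows in SAP 7.1.3 run to Day 183. The text of Protocol 9.3.3.1 places VISIT 10 "169 days after the initial dose of the study medication for the Treatment", which is Study Day 170 under SAP 7.1.2 although the heading says Day 169; the two need to be reconciled. If most women take a tablet on Day 169 or later, the bias is small. A reader might infer from the planned schedule that nobody is dosed after Day 168, so that the any-TEAE row must read 100%. The documents do not support that: f = 0 is unlikely, and even then 100% follows only under reading A. Under reading B with the same assumptions the value would be 0.20/0.52 = 38%.

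**Occurrence may include ongoing events.** This also stands. The table (9) rules first say that a TEAE occurring in several intervals counts in each, and only the numerator sentence uses the word onset. A reader might infer that the percentage can never be too low. That holds under reading A only. Under reading B, an early discontinuer whose TEAE was recorded as ongoing could enter the last denominator after her own AE collection had ended, which pulls the percentage down. The upward direction is expected, not guaranteed.

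**It is one descriptive column.** True. No test uses table (9), and the other TEAE tables do not use this denominator. That limits the consequence but does not justify the rule.

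**Another document may correct it.** SAP 7.2 refers to the Handling Rules for Analysis Data, which were not available for this review. Nothing in the protocol or SAP corrects the rule, and SAP 7.11.1.2 states this denominator explicitly.

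**Conclusion.** The concern holds within limits. As written, the rule makes entry to the Day 169-to-Max denominator depend on the outcome for every woman not dosed on or after Day 169. The percentages in that column are therefore expected to be too high.

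The rule and its effect on the denominator follow from the text; the size does not. Over the assumed range, a true 20% could appear as anything from about 21% (f = 90%, either reading) to 50% (f = 25%, onset reading, independence), and nothing in the documents says where in that range the trial would fall.

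Women whose AE collection ended before Day 169 are rightly left out. The same rule touches earlier intervals through early discontinuers, but to a much smaller degree. The counts of women by onset, the other TEAE tables and all efficacy results are unchanged.

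**What to change.** In SAP 7.11.1.2, replace the at-risk definition for table (9):

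- **Denominator:** for each interval, all safety-set subjects still under routine AE collection on or after the interval's first day, regardless of dosing or TEAE. Routine collection runs to VISIT 11, or to the last AE assessment if that is earlier. Telephone contact about menstruation recovery (Protocol 9.1.21) does not count.
- **Numerator:** those at-risk subjects with a TEAE onset in the interval.
- **Footnote:** any event reported with onset after routine collection ended, such as a related SAE reported later under Protocol 10.2.2.
- **Label:** mark the Day 169-to-Max column as mainly post-treatment follow-up and print its denominator.

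Using the last AE assessment also covers women who stop early. For them Protocol 10.2.1.1 can be read as ending collection at early termination, while Protocol 9.3.4.1 schedules an AE assessment 28 days after the end of treatment.

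The cost is a few SAP sentences and a small programming change, using visit, disposition and onset dates already collected. One weakness remains: follow-up within the last column is of unequal length, since a woman whose VISIT 11 falls on Day 169 counts the same as one followed for 28 days. A footnote should say so.

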7.11.1.3 Displays of Pretreatment Events

Analysis Set: All Subjects Who Signed the Informed Consent Form

Analysis

Variable(s) : Pretreatment event (PTE)

Analytical The following summaries will be provided using frequency distribution.

Method(s) : PTEs will be coded using the MedDRA and will be summarized using SOC and PT. SOC will be sorted alphabetically and PT will be sorted in decreasing frequency.

- (1) Pretreatment Events by System Organ Class and Preferred Term
- (2) Serious Pretreatment Events by System Organ Class and Preferred Term

The frequency distribution will be provided according to the rules below.

Number of subjects

A subject with multiple occurrences of PTE within a SOC will be counted only once in that SOC. A subject with multiple occurrences of PTE within a PT will be counted only once in that PT.

7.11.1.4 Displays of Run-in Adverse Events

Analysis Set: All Subjects Who Received Run-in Study Drug

Analysis

Variable(s) : Run-in AE

Analytical The following summaries will be provided using frequency distribution.

Method(s) : Run-in AEs will be coded using the MedDRA and will be summarized using SOC and PT. SOC will be sorted alphabetically and PT will be sorted in decreasing frequency.

- (1) Run-in Adverse Events by System Organ Class and Preferred Term
- (2) Drug-Related Run-in Adverse Events by System Organ Class and Preferred Term
- (3) Serious Run-in Adverse Events by System Organ Class and Preferred Term

The frequency distribution will be provided according to the rules below.

Number of subjects

A subject with multiple occurrences of run-in AE within a SOC will be counted only once in that SOC. A subject with multiple occurrences of run-in AE within a PT will be counted only once in that PT.

7.11.2 Clinical Laboratory Evaluations

7.11.2.1 Hematology and Serum Chemistry

Analysis Set: Safety Analysis Set

Analysis

Variable(s) : Hematology

RBC	Platelets	WBC
WBC Differentials (Neutrophils, Eosinophils, Basophils, Lymphocytes, Monocytes)		

Serum Chemistry

ALT	AST	Lactate dehydrogenase (LDH)
Gamma glutamyl transferase (GGT)	Albumin	Alkaline phosphatase (ALP)
Bilirubin (Total bilirubin)	Protein (Total protein)	Cholesterol (Total cholesterol)
High density lipoprotein (HDL) cholesterol	Low density lipoprotein (LDL) cholesterol	Triglycerides
Glucose	HGB A1C	Creatinine
Blood urea nitrogen (BUN)	Creatine kinase	Urate
Sodium	Potassium	Chloride
Calcium	Phosphate	Magnesium
Bile acid (total bile acid [TBA])	Glutamate dehydrogenase (GLDH)	

Visit: Baseline, Week 2*, 4, 8, 12, 16, 20, 24 and Follow-up

*: only TBA and GLDH

Analytical

Method(s) : For each variable, summaries (1) to (3) will be provided by treatment group.
For applicable variables, summaries (4) and (5) will be provided by treatment group.

- (1) Summary of Laboratory Test Results and Change from Baseline by Visit
Descriptive statistics for observed values for each visit and changes from baseline will be provided.
- (2) Case Plots
Plots over time for each subject will be presented.
- (3) Summary of Shifts of Laboratory Test Results
Shift tables showing the number of subjects in each category at baseline and each post-baseline visit will be provided.
For each laboratory test, the laboratory values will be classified as "Low", "Normal" or "High" relative to the normal reference range provided by the central laboratory. The shift tables will be based on these classifications.
- (4) Number and Percentage of Subjects with Markedly Abnormal Values of Laboratory Parameters
Overall frequency distributions of MAV during treatment period will be provided. If a laboratory parameter has both lower and upper MAV criteria, analysis will be performed for each. Further details are given in Appendix.
- (5) Number and Percentage of Subjects with Elevated Liver Enzyme Laboratory Parameters
Overall frequency distributions of elevated hepatic parameters during treatment period will be provided. Further details are given in Appendix.

7.11.2.2 Urinalysis

Analysis Set: Safety Analysis Set

Analysis

Variable(s) : Protein [-, +-, 1+, 2+, 3+, 4+]
Glucose [-, 1+, 2+, 3+, 4+, 5+]
Occult blood [-, +-, 1+, 2+, 3+]
Bilirubin [-, +-, 1+, 2+, 3+]
Urobilinogen [+-, 1+, 2+, 3+]

Visit: Baseline , Week 4, 8, 12, 16, 20, 24 and Follow-up

Analytical

Method(s) : For each variable, summaries (1) and (2) will be provided by treatment group.

(1) Number of Subjects in Categories of Urine Laboratory Test Results

Shift tables showing the number of subjects in each category at baseline and each post-baseline visit will be provided.

(2) Summary of Shifts of Urine Laboratory Test Results

Shift tables showing the number of subjects in each category at baseline and each post-baseline visit will be provided.

For each urine laboratory test, the laboratory values will be classified as "Normal" or " Abnormal " relative to the normal reference range provided by the central laboratory. The shift tables will be based on these classifications.

7.11.3 Vital Signs

7.11.3.1 Vital Signs and Weight

Analysis Set: Safety Analysis Set

Analysis

Variable(s) : Systolic Blood Pressure
Diastolic Blood Pressure
Pulse Rate
Body temperature
Weight

Visit: Baseline , Week 4, 8, 12, 16, 20, 24 and Follow-up

Analytical

Method(s) : For each variable, summaries (1) and (2) will be provided by treatment group.

For applicable variables, summary (3) will be provided by treatment group.

(1) Summary of Vital Signs Parameters and Weight and Change from

Baseline by Visit

Descriptive statistics for observed values for each visit and changes from baseline will be provided.

(2) Case Plots

Plots over time for each subject will be presented.

(3) Number and Percentage of Subjects with Markedly Abnormal Values of Vital Signs Parameters

Overall frequency distributions of MAV during treatment period will be provided. If a vital sign parameter has both lower and upper MAV criteria, analysis will be performed for each. Further details are given in Appendix.

7.11.4 12-Lead ECGs

7.11.4.1 12-lead ECG

Analysis Set: Safety Analysis Set

Analysis

Variable(s) : 12-lead ECG Interpretation [Within Normal Limits, Abnormal but not Clinically Significant, Abnormal and Clinically Significant]

Visit: Baseline , Week24 and Follow-up

Analytical

Method(s) : For 12-lead ECG interpretation, summary (1) will be provided by treatment group.

(1) Summary of Shift of 12-lead ECG Interpretation

Shift table showing the number of subjects in each category at baseline and each post-baseline visit will be provided.

